3.7 Analyses

Unit of Analysis and Sample Size Calculation

Patients within pairs (peer-peer coach dyads) will be the primary unit of analysis for the study. Thus, we calculated the sample size to adjust for the likely correlation between members of the pairs (intraclass correlation, or rho) in the intervention group. Accordingly, we calculated the sample size to provide 80% power to detect a difference between experimental groups of 0.5% in A1c with an alpha of .05, two-tailed.[95] We conducted the power analysis using the methods of Cohen and, based on the within-pair ICC of our prior reciprocal peer support intervention, adjusted for a within-pair intraclass correlation of 0.03 as implemented in STATA 12 software.[96] We estimated the standard deviation of a decline in A1c in this population (1.45) using data from our prior randomized controlled trials.[9,40] To provide the needed power, 148 subjects will be needed in each group (after attrition) and 74 peer mentors (clusters) across both groups (37 in each group). To conservatively allow for up to 15% attrition, a rate higher than occurred in any of our prior VA diabetes RCTs, we will recruit 174 patients for each arm, for a total of 348 patients, and a total number of 87 peer mentors. The estimate of the standard error of the change in BP was estimated from a database of actual BPs obtained in routine clinical practice for 24,000 patients with diabetes and hypertension in one large service network in the VA over a 24-month period in FY 2004-2005. It depends on both the variation in BP change at the person level and variability within person between measurements. We estimated the standard error for the change in blood pressure as 17 mmHg. Our target sample size will provide 90% power to detect a difference between experimental groups of 5 mmHg and differences between each of our key patient-centered outcome measures.

Approach to All Analyses

We will follow international guidelines for analysis and reporting of clinical trials.[97] In the first phase (data verification), we will examine the distribution of all study variables to assess extreme values, missing data, variances, possible coding errors, skewness, and type of distribution. We will examine baseline data for clinically important differences across the two study groups for potential prognostic indicators, such as patients' age, race, comorbidities, and baseline use of services. Although we do not anticipate any imbalances due to the randomization, any differences between experimental arms in baseline characteristics will be included as covariates in analyses comparing outcomes. In the second phase of our outcomes analyses, we will evaluate possible bivariate associations between patients' experimental condition and the outcomes, as well as between each covariate and the outcomes, prior to fitting multivariable models. This will be done to determine unadjusted measures of effect, assess possible confounders, and anticipate any collinearity in subsequent analyses. In the final phase we will fit multivariable models to identify main effects.

Analysis Plans by Aim

Aim 1: Test the effectiveness of a technology-enhanced peer coaching (TEC) program in improving glucose control relative to peer support alone. Our past experience in similar patient populations

suggests that the primary endpoint from the trial (change in A1c) will be close to normally distributed. To assess the primary endpoint for Specific Aim 1 (change in mean HbA1c from baseline to 6 months), we will use a general linear mixed regression model:

where i represents the patient, I represents the intervention, j is the pair-group, β_l are parameters estimated from the data, X_{il} is the value of the l th fixed effect (peer support versus usual care) for the i th patient, β_j are parameters estimated from the data, Z_{ij} is the value of the j th random effect (pairs) for the i th patient, and ϵ_i is the residual error.[99] We anticipate that members of peer coach-peer partner pairs in both arms, because of their interactions with each other, might show a positive intraclass correlation (ICC), a component of the variance attributable to the group. As recommended for group-randomized trials, the mixed model analyses will thus address potentially inflated type I errors that could occur if such clustering were not taken into account.[97] If patients in either arm drop out of the study or request reassignment to another peer coach, they will be analyzed according to their initial pairing in an intent-to-treat analysis.

After unadjusted changes in A1c are determined, further analyses using mixed-model ANCOVA will adjust for confounding effects of any variables that differed substantially between treatment arms. Both unadjusted and adjusted means with 95% confidence intervals will be reported for both arms. While the primary endpoint is the mean difference between baseline and 6-month A1c concentrations, subsequent analyses will be conducted to determine whether the intervention additionally affects the difference between baseline and 12-month A1c (i.e., the sustainability of any treatment effects) using a repeated-measures mixed model ANCOVA.

We will follow the same approach to comparing the observed usual care group with the peer support alone group. However, there is a higher likelihood of imbalances as the usual care group is observational, although they are drawn from the same eligibility pool as the participants. Therefore, we will include several key covariates in the analysis, including baseline A1c, age, gender, and race. We will also examine the data for differences in other potential prognostic indicators, such as baseline medication or service use, and include these variables in the regression if necessary. We will also need to examine whether biases may be caused by missing A1c data. Although the very high level of A1c testing in VHA is likely to lead to few missing data points, we will conduct sensitivity analyses using two approaches. In the first, we will assume that those with missing A1c levels at the end of the study had no improvement in their A1cs. In the second, we will use multiple imputation methods to fill in missing A1c values.

Aim 2: Assess the impact of the intervention on blood pressure and medication adherence as well as on key patient-centered outcomes, including patients' satisfaction and involvement with care, perceived social support, and diabetes-specific quality of life. For assessment of changes in systolic blood pressure and for the self-reported outcomes, we will use mixed effects models (similar to those in Aims 1) for

continuous outcomes, and generalized estimating equations (GEE) for ordinal outcomes with clustering.[98]

Aim 3: Identify patient characteristics associated with engagement in the intervention and mediators and moderators of the intervention's impact on patient outcomes. For these analyses, we will use multivariate modeling and path analyses.[99] Many of these outcomes will be measured using Likert scales. Thus, we will begin these analyses by developing contingency tables for ordered categorical data. We will then use generalized estimating equations (GEE), which are appropriate for modeling ordinal outcomes with correlated data.[99]

We will use both quantitative and qualitative methods. We will compare patient characteristics and attitudes of participants and those not willing to participate in the study. For example, using VA administrative data, we will compare the characteristics of study participants (mean age, race, most recent A1C, co-morbidities) with those of diabetes patients treated in each site's outpatient clinics. Eligible refusals will be asked whether they would consent to a brief survey in which we will record information helpful in assessing the intervention's reach, such as diabetes distress, perceived need for support, interpersonal attachment styles, reasons for not enrolling, and existing sources of social support.

We will model independent associations and pathways linking intervention exposure to outcomes using nested multivariate regression. Subsequent nested models will introduce potential mediators, and we will evaluate changes in the magnitude of the relationship between experimental condition and outcomes before and after the covariates are introduced. Analyses of potential moderators will use standard approaches to evaluate potential interactions between these covariates and patients' experimental condition.[100] Independent variables and moderators will be centered before testing interactions, so that multicollinearity between first order and higher-order terms will be minimized. Statistically significant interactions will be interpreted by plotting regression lines for high and low values of the moderator variable. Stata routines greatly facilitate the plotting of these relationships.[101]

To gain more in-depth understanding of factors associated with level of engagement in the intervention and with outcomes, along with examining baseline correlates of different levels of engagement using quantitative approaches with the baseline survey and clinical data, we will conduct and analyze semi-structured interviews conducted at the 6-month assessment. The use of the IVR platform will enable us to categorize patient-mentor dyads into different levels of frequency of contacts and duration of contacts ("engagement"). The IVR system records data on dates of all completed telephone contacts and duration of each telephone call into a data set in separate data fields. It is thus easy to examine the 'dose' of intervention engagement of each dyad, depending on how frequently and how long they spoke together. We will conduct semi-structured interviews with purposive samples of peer mentors and participants with different levels of intervention engagement (low, medium, and high). We will perform

a thematic analysis of the interview data with participants with different levels of engagement in the intervention (in both arms) using QSR NVivo, a qualitative data analysis package. Our overall approach to thematic analysis will be what Miller and Crabtree refer to as the “Editing Analysis Style,” which contains both deductive and inductive elements. Following this approach, two investigators will independently read interview transcripts, break down patient interview responses into individual segments that express a single idea or theme (e.g., particular ways respondents found the telephone calls useful or not useful) and label these phrases with appropriate codes. An iterative process will be used to compare results until agreement is reached on the categories and criteria for inclusion.[102] We will seek to examine in more depth factors contributing both to successful and unsuccessful peer mentor-partner matches.

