## Measures and Data Collection

### Overview

Measurement will occur at baseline, 6 months (at the completion of the intervention), and 12 months after enrollment. Variables chosen for measurement are based on our conceptual framework (Section 3.4.1). At baseline, 6 months, and 12 months, patients (participants and peer mentors) will complete a written survey and assessments of A1c and blood pressure. Patients will receive \$25 for each assessment they complete. To understand features of successful vs. less successful peer partnerships, we will conduct semi-structured telephone interviews at 6 months of a purposive sample of participants and mentors in both study arms (choosing a sample with high rates of contact and a sample with low rates of contact). Using standard qualitative methods for identifying key themes in participant's experiences with this new program, we will identify central themes from these interviews associated with the success of the peer relationships and in meeting intervention goals. Participants and peer mentors in the peer mentor +iDecide arm will be asked about their experiences with iDecide and how use of the program affected their subsequent contacts and activities (e.g., setting and meeting 'action plan' goals, effectively raising questions and concerns with PCPs). Quantitative information about use of the IVR system will be collected via computerized records that the system maintains of all contacts with dates and time durations of all contacts as well as of attempted contacts. To assess peer mentors' experiences, we will conduct semi-structured interviews with a purposive sample of peer mentors with differing rates of participation (e.g., those who made regular contact with their assigned peers vs. those who did not).

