### 3.6.2 Description of Measures by Aim

**Aim 1:** Test the effectiveness of a technology-enhanced peer coaching (TEC) program in improving glucose control relative to peer support alone. At baseline, 6 months, and 12 months, a trained staff member will measure patients' A1c, using a Bayer DCA 2000+ analyzer, a portable analyzer producing A1c assays in approximately six minutes using finger stick blood samples. These assays have a test coefficient of variation (CV, measure of test precision) <5% as required by the National Diabetes Data Group and accurately measure A1c levels.[78] The DCA 2000 is reliable, easy to use, and much less burdensome to patients than venous blood draws. Our team has familiarity with the DCA 2000 from our prior studies.[40,56] To ensure quality control, venous A1c samples will be drawn from 5% of participants and analyzed at the Detroit VA's lab.

For our "usual care" observed group, we will use CDW data to measure A1c levels. More than 85% of diabetes patients who meet our eligibility criteria receive A1c testing at recommended intervals, which should ensure adequate numbers of patients with follow-up A1c levels in our control sample. For those with missing A1c data, we will use several approaches to examine possible biases (see section 3.7.5).

**Aim 2:** Assess the impact of the intervention on blood pressure and medication adherence as well as on key patient-centered outcomes, including patients' satisfaction and involvement with care, perceived social support, and diabetes-specific quality of life. These measures will be assessed at baseline, 6 months, and 12 months. We will measure blood pressure using an Omron® automatic blood pressure

monitor with memory and take the average of the two readings following American Heart Association guidelines. (Ideally we would also measure lipid levels, but have not found sufficiently reliable point-of-service machines for these measurements. At baseline we will collect information on most recent LDL, HDL, and total cholesterol levels from electronic medical records. If there are no recent values, the iDecide program text in that section will emphasize the importance of having these risk factor levels checked.) The baseline and 6-month surveys will take approximately 25 minutes to complete, and the 12-month survey will take approximately 15 minutes. Measures for the key patient-centered outcomes are:

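### The claimed 90% power for a 5 mmHg blood-pressure difference does not follow from the SAP's own inputs, which give about 72% at 148 per arm and 78% at 174 per arm before clustering

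*SAP*

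**What the plan says.** SAP section 3.7 (Unit of Analysis and Sample Size Calculation) bases the sample size on HbA1c: "80% power to detect a difference between experimental groups of 0.5% in A1c with an alpha of .05, two-tailed", with an SD of 1.45 and a within-pair ICC of 0.03. This leads to 148 patients and 37 mentors per arm after attrition, and 174 patients per arm recruited.

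The same paragraph then turns to BP. The variability comes from a "database of actual BPs obtained in routine clinical practice for 24,000 patients with diabetes and hypertension", and the SAP says of it: "It depends on both the variation in BP change at the person level and variability within person between measurements". The value given is: "We estimated the standard error for the change in blood pressure as 17 mmHg". The conclusion drawn is: "Our target sample size will provide 90% power to detect a difference between experimental groups of 5 mmHg". The same sentence extends the claim to the key patient-centered outcomes, without an effect size or SD for any of them.

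No alpha, ICC, baseline correlation, follow-up contrast or formula is stated for BP. On timing, the Protocol Overview says: "Measurement will occur at baseline, 6 months (at the completion of the intervention), and 12 months after enrollment".

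**The concern.** One sample is said to give 80% power for a standardized difference of 0.34 and 90% power for a standardized difference of 0.29. With the same test, alpha and clustering, power falls as the standardized effect shrinks, so the two statements cannot both hold.

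This sentence is the only statement of power for the Aim 2 outcomes. If it stands, a null BP result could be read as good evidence against a 5 mmHg effect, when the stated inputs leave a chance of missing that effect of more than one in four at 148 per arm. They leave more than one in five at 174.

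**Working it through.** **Inputs from SAP section 3.7.** BP difference 5 mmHg; BP variability 17 mmHg; 148 per arm evaluable and 174 per arm recruited; 37 mentors per arm; ICC 0.03 (stated for HbA1c); HbA1c difference 0.5 and SD 1.45; alpha 0.05 two-sided (stated for HbA1c).

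**Two assumptions.**
- 17 mmHg is the SD of individual change, although it is labelled a standard error. Its description, person-level variation in change plus within-person variability, fits an SD. Taken literally as the standard error of the difference between arms, it would give power of Φ(5/17 − 1.96), about 5%.
- Two-sided 0.05 also applies to BP.

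**Step 1: reproduce the HbA1c size.** With design effect DE, n per arm = 2 × (1.96 + 0.8416)² × (1.45/0.5)² × DE.
- DE = 1: 132.0, or 133 rounded up.
- DE = 1 + (4 − 1) × 0.03 = 1.09, from 148/37 = 4 patients per mentor: 143.9.
- DE = 1 + (5 − 1) × 0.03 = 1.12, counting the mentor as a fifth member: 147.9, against 148 stated.

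The method reproduces the plan's primary calculation.

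**Step 2: compare the two effects.** HbA1c: 0.5/1.45 = 0.345. BP: 5/17 = 0.294. Even the larger HbA1c effect, at 174 per arm with no attrition and no clustering, has power Φ(0.345 × √(174/2) − 1.96) = 0.8955, just under 90%.

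**Step 3: BP power, unadjusted change at one follow-up.** Power = Φ((5/17) × √(n/(2·DE)) − 1.96). For n = 148 and DE = 1 this is Φ(2.530 − 1.96) = 0.716; for n = 174, Φ(2.743 − 1.96) = 0.783.

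| n per arm | DE 1.00 | DE 1.09 | DE 1.12 |
|---|---|---|---|
| 148 | 71.6% | 67.8% | 66.7% |
| 174 | 78.3% | 74.8% | 73.6% |

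The noncentral t gives 71.3% and 78.1% at DE = 1.

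**Step 4: what 90% would need.**
- Sample size: 2 × (1.96 + 1.2816)² × (17/5)² × DE = 243 per arm at DE = 1, 265 at 1.09 and 272 at 1.12.
- SD: 5/(3.2416 × √(2/n)) = 13.3 mmHg at 148 per arm and 14.4 mmHg at 174, without clustering.
- Detectable difference at 148 per arm, (1.96 + z) × 17 × √(2·DE/148) for DE 1.00 to 1.12: 5.5–5.9 mmHg at 80% power and 6.4–6.8 mmHg at 90%.

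**Step 5: other readings.** Let v be the variance relative to a single change score, and r the correlation between any two visits. Equal variances and equal correlations are assumed. Power is without clustering unless noted.

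| Reading | 148 per arm | 174 per arm |
|---|---|---|
| One-sided 0.05, single change | 81.2% | 86.4% |
| Mean of 6- and 12-month changes, v = 1.5(1 − r)/(2(1 − r)) = 0.75 | 83.2% | 88.6% |
| Baseline-adjusted, one follow-up, v = (1 + r)/2 | 90% only if r ≤ 0.22 | 90% only if r ≤ 0.43 |
| Averaged and baseline-adjusted, v = ((1 + r)/2 − r²)/(2(1 − r)); r = 0.5 gives v = 0.50 | 94.7% (92–93% clustered) | 97.3% |

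Counting mentors as analysed patients gives 148 + 37 = 185 per arm, or 174 + 87/2 ≈ 217 as recruited. A single change score then has 80.8% and 86.5% power.

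**The case against.** The strongest reply is that 72% describes one particular analysis, while the SAP plans mixed models for BP that resemble those of Aim 1. Those include an adjusted model and a repeated-measures ANCOVA. Averaging both follow-ups and adjusting for baseline BP passes 90% at r = 0.5, even with clustering. Counting mentors and averaging follow-ups also reaches 90.4% at 185 per arm without clustering (87–88% with it). The trial's BP may also be less variable than routine readings, because staff use a "monitor with memory and take the average of the two readings following American Heart Association guidelines". Further, the Aim 1 equation is not legible in the text available, and its legend leaves room for more than one fixed effect.

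Part of this stands. The result does not show that 90% is out of reach, and only the sponsor can confirm from its database what the 17 mmHg represents. It does not rescue the sentence as written. The SAP ties the repeated-measures model to whether the HbA1c effect persists to 12 months, not to an averaged BP effect. Covariates are to be added where the arms differ at baseline, and baseline BP is not named. No BP correlation and no SD below 17 mmHg is given. The routes in the working that reach 90% either combine choices the SAP does not make for BP or need a low baseline correlation it does not state.

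**Conclusion.** The concern holds. On the stated inputs the power for 5 mmHg is about 72% at 148 per arm and 78% at 174 before clustering, which is 18 and 12 points below the claim. If the HbA1c ICC is assumed for BP, it is 67–68% and 74–75%.

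These figures assume that 17 mmHg is an SD of individual change, that alpha is two-sided 0.05, and that the comparison is of unadjusted change at one follow-up. The inconsistency with the HbA1c calculation needs only the SD reading and a common test. It does not depend on the value of the ICC or on which of the two sample sizes was meant.

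BP is a secondary outcome, and neither enrolment nor HbA1c power changes, so this should be fixed but is of moderate weight. The 90% for the patient-centered outcomes cannot be checked at all; that is missing detail rather than an arithmetic error.

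**What to change.** Confirm against the source database that 17 mmHg is the SD of individual BP change and label it so. Then take one of two routes.

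1. **Default: replace the claim.** Suggested text: *With 148 evaluable patients per arm, an SD of BP change of 17 mmHg and two-sided alpha 0.05, an unadjusted comparison of change at one follow-up has about 72% power for 5 mmHg before clustering, and about 67–68% if an ICC of 0.03 is assumed (design effect 1.09–1.12). The detectable difference is 5.5–5.9 mmHg at 80% power and 6.4–6.8 mmHg at 90%, the ranges covering design effects from 1.00 to 1.12.*
2. **Keep a higher figure** only if the SAP pre-specifies the BP analysis that gives it (baseline BP as a covariate, averaged follow-ups, or both) and states the n, SD, correlation and design effect used.

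For the patient-centered outcomes, withdraw the blanket 90% or replace it with a detectable standardized effect. For a continuous scale at 148 per arm before clustering this is (1.96 + z) × √(2/148) = 0.33 SD at 80% power and 0.38 SD at 90%. Outcomes analysed as ordinal by GEE would need their own statement.

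The cost is SAP wording only, with no added enrolment. The stated secondary-outcome power becomes less favourable or gains explicit assumptions.

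### The randomized A1c comparison does not fix baseline A1c as a covariate or say whether the unadjusted or adjusted result is primary; naming one baseline-adjusted primary model would settle both.

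*SAP*

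**What the plan says.** All of this is in SAP section 3.7.

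- **Approach to All Analyses.** Baseline data are screened for "clinically important differences across the two study groups for potential prognostic indicators", with age, race, comorbidities and service use as the examples. Then "any differences between experimental arms in baseline characteristics will be included as covariates in analyses comparing outcomes". A last phase fits multivariable models.
- **Analysis Plans by Aim, Aim 1.** The primary endpoint, change in A1c from baseline to 6 months, is assigned to a general linear mixed model. The equation is missing from the available text. Its legend names one "fixed effect (peer support versus usual care) for the i th patient" and a random effect for pairs. That contrast is not Aim 1's randomized one, which is technology-enhanced coaching versus peer support alone.
- **Aim 1, adjustment.** Once unadjusted changes are available, "further analyses using mixed-model ANCOVA will adjust for confounding effects of any variables that differed substantially between treatment arms". On reporting: "Both unadjusted and adjusted means with 95% confidence intervals will be reported for both arms".
- **Aim 1, usual-care comparison.** For this observational comparison "we will include several key covariates in the analysis, including baseline A1c, age, gender, and race".
- **Aim 2.** For systolic blood pressure and the self-reported outcomes, "we will use mixed effects models (similar to those in Aims 1) for" the continuous ones.

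**The concern.** There are two linked gaps.

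First, no visible sentence commits the randomized comparison to baseline A1c as a covariate. Taking change as the outcome is not the same as adjusting for baseline. The change score forces the baseline coefficient to one, whereas a covariate lets the data estimate it, which usually narrows the interval. Protocol 3.6.2 has A1c measured at baseline, so the covariate is already collected. Adjusting only when an imbalance is seen recovers part of the gain, and how much depends on a trigger to which the SAP gives no number.

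Second, neither result is expressly primary. The order of the Aim 1 text suggests that the unadjusted result leads. The general section says that differing characteristics enter the outcome comparisons and that multivariable models identify main effects. Two analysts following this text could lead with different results, and the choice could be made after the data are seen.

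The continuous Aim 2 outcomes use the same model form and inherit both gaps.

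**Working it through.** **Inputs from the SAP (Unit of Analysis and Sample Size Calculation).** Difference 0.5%, SD of the A1c change 1.45, two-sided alpha 0.05, power 80%, ICC 0.03, 148 patients and 37 mentors per arm, hence 148/37 = 4 patients per mentor.

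**Inputs assumed, because the documents give neither.** r is the correlation between baseline and 6-month A1c, taken as 0.3 to 0.8. k is the baseline SD divided by the 6-month SD, taken as 1 or 0.8. The change SD is held at 1.45.

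**Step 1: the plan's own figure.** 2 × (1.45 × (1.960 + 0.842)/0.5)² = 132.02, so 133 per arm. The design effect is 1 + (4 − 1) × 0.03 = 1.09. Then 133 × 1.09 = 144.97, or 145, which rounds up to 37 whole clusters of 4 = 148. The stated 148 reproduces from the change-score SD, with no gain from baseline adjustment built in.

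**Step 2: change-score power at 148 per arm.** The standard error is 1.45 × √(2 × 1.09/148) = 0.176. The standardized effect is 0.5/0.176 = 2.841. Power is Φ(2.841 − 1.96) = 81.1%. The 95% half-width is 1.96 × 0.176 = 0.345%.

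**Step 3: baseline A1c always included.** The variance ratio of the adjusted estimate to the change score is q = (1 − r²)/(k² + 1 − 2rk). Power is Φ(2.841/√q − 1.96).

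| r | q, k = 1 | Power, k = 1 | q, k = 0.8 | Power, k = 0.8 |
|---|---|---|---|---|
| 0.3 | 0.65 | 94% | 0.784 | 89% |
| 0.5 | 0.75 | 91% | 0.893 | 85% |
| 0.7 | 0.85 | 87% | 0.981 | 82% |
| 0.8 | 0.90 | 85% | 1.000 | 81% |

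At r = 0.5 the half-width falls from 0.345% to 0.345 × √0.75 = 0.299% (k = 1) or 0.345 × √0.893 = 0.326% (k = 0.8). When r = k, q = 1 and there is no gain.

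**Step 4: adjustment only on imbalance.** Suppose the adjusted result replaces the unadjusted one when the baseline A1c difference has |t| above a trigger. Write Z_change = ρ·Z_base + √q·Z_adjusted, with Z_base and Z_adjusted independent and ρ = (r − k)/√(k² + 1 − 2rk), and integrate over Z_base. At r = 0.5, k = 1:

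| Trigger on baseline \|t\| | Power | Type I error |
|---|---|---|
| 0 (any difference at all) | 91% | 5.0% |
| 0.5 | 88% | 4.1% |
| 1.0 | 86% | 3.7% |
| 1.5 | 84% | 3.9% |
| 1.97 | 82% | 4.3% |

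Over all the r, k and trigger values, type I error is 3.2% to 5.0%. The rule does not inflate it.

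**Step 5: lead result chosen afterwards.** If both analyses are always run and either significant result may lead, type I error is 5.0% to 7.8% over the grid (7.3% at r = 0.5, k = 1). If the adjusted result exists only when |t| > 1.5, it is 5.3% at r = 0.5, k = 1.

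**Step 6: balance by design.** The randomization section is not in the available text, so balancing on A1c cannot be excluded. In the limit of perfect balance at r = 0.5, k = 1, the unadjusted test has type I error 2Φ(−1.96/√0.75) = 2.4% and power Φ((2.841 − 1.96)/√0.75) = 85%, against 91% when baseline is always in the model.

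**The case against.** The strongest reply is that the SAP already ranks the results. The Aim 1 text ties one mixed model to the primary endpoint and calls the ANCOVA work further analysis, and the sample size was built on the unadjusted change SD. That reading is reasonable and the Aim 1 text is the more specific. It remains an inference from order, and the general section points the other way.

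A second reply is that, if every baseline difference however small triggers adjustment, baseline A1c would always enter and no precision is lost. The trigger-0 row agrees. But the same section screens for clinically important differences and Aim 1 asks for substantial ones, so this is not the natural reading. It also conflicts with the first reply, under which the unadjusted result leads.

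Third, the missing equation might contain a baseline term. That cannot be ruled out. The legend is weak evidence either way because it names the wrong contrast, so the point is limited to the visible text. The missing ranking rests on prose that is present.

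Fourth, the benefit depends on r and k. This stands. For r of 0.3 to 0.8, k = 0.6 gives 82% to 85% power and k = 1.2 gives 93% to 97%. The table also applies the same design effect before and after adjustment. If clustering by mentor arises only after baseline, the k = 1 column becomes 93/90/86/85%, a slightly smaller gain.

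Finally, the 5.0% to 7.8% figure describes a choice that the SAP does not endorse, and reporting both results would make any such choice visible. That also stands. The figure shows what an unnamed primary result permits, not what the plan does.

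**Conclusion.** The concern holds as a matter of precision and pre-specification. No visible text fixes baseline A1c for the randomized comparison, and no sentence makes the unadjusted or the adjusted result primary. The change-score test is valid, 148 per arm is adequate, and the imbalance-driven rule does not raise type I error.

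Against 81% power by change score, always adjusting gives 85% to 94% at k = 1 and 81% to 89% at k = 0.8. The benefit therefore runs from nothing to about 13 percentage points. These figures rest on assumed r and k, a change SD of 1.45, a design effect of 1.09 and, except in Step 6, no balancing of A1c by design. The undefined lead result does not depend on r or k; only its possible cost does.

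**What to change.** In SAP 3.7, Aim 1, name one primary model for the randomized comparison: arm (technology-enhanced coaching versus peer support alone), baseline A1c as a fixed covariate whatever the observed balance, and the clustering random effect. State that its arm estimate and 95% confidence interval are the primary result. Adding the covariate alone does not settle the ranking, so label the unadjusted result and any imbalance-driven model as sensitivity analyses. If imbalance-driven adjustment is kept, give its numeric threshold. Correct the fixed-effect legend so that it names the randomized contrast. Include the baseline value in the same way for continuous Aim 2 outcomes measured at baseline.

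The cost is SAP wording and one degree of freedom per model. With 294 rather than 293 degrees of freedom the critical t is 1.968 either way; at cluster level, 72 to 71, it moves from 1.9935 to 1.9939. Sample size, visits and data collection do not change.
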